16. DATA HANDLING AND RECORDKEEPING

16.1. **Inspection of Records**

As noted in Section 13.6, it is the responsibility of the PI and the participating institution to assure that appropriate trial-related monitoring, audits, IRB/EC review, and regulatory inspection(s) can be carried out by assuring direct access to source data/documents. These inspections may be conducted by Soligenix or its designee or representatives of the FDA, EMA, or local Health Agencies.

16.2. **Retention of Records**

It is the joint responsibility of both the site PI and the institution to take measures to prevent accidental or premature destruction of all study documents including the source documents. Essential documents should be retained until at least 2 years after the last approval of a marketing application in an ICH region and until there are no pending or contemplated marketing applications in an ICH region; at least 2 years have elapsed since the formal discontinuation of clinical development of the investigational product; or 7 years since the close-out of the clinical trial. Soligenix will inform the investigator/institution as to when these documents no longer need to be retained.

If the responsible investigator retires, relocates, or for other reason withdraws from the responsibility of keeping the study records, custody must be transferred to a person who will accept the responsibility. Soligenix must be notified in writing and approve of the name and address of the new custodian.

16.3. **Publication Committee**

The Sponsor, Soligenix, is committed to the prompt publication of the results of this trial regardless of the outcome. A Publication Committee will be appointed to review and prepare a manuscript for submission to an appropriate peer-reviewed scientific journal. Membership to the committee will be offered, at a minimum, to the study's PI, the 6 sites enrolling the highest number of evaluable patients into the trial, the study statistician, and representatives of Soligenix. Other members may be appointed at the initial Publication Committee meeting.

Confidential

# LIST OF ABBREVIATIONS

AE	Adverse Event
ALT	Alanine Aminotransferase
AST	Aspartate Aminotransferase
AUC	Area-Under-the-Curve
BMI	Body Mass Index
BUN	Blood Urea Nitrogen
СР	Conditional Power
CRT	Chemoradiation Therapy
CTCAE	Common Terminology Criteria for Adverse Events
eCRF	Electronic Case Report Form
EORTC	European Organization for Research and Treatment of Cancer
HCG	Human Chorionic Gonadotropin
HNC	Head and Neck Cancer
HPV	Human Papillomavirus
ITT	Intent-to-Treat
IV	Intravenous
MedDRA	Medical Dictionary for Regulatory Activities
mITT	Modified Intent-to-Treat
n	Number
NCI	National Cancer Institute
OM	Oral Mucositis
PD	Protocol Deviation
PI	Principal Investigator
QLQ-H&N43	Quality of Life Question for Head and Neck Cancer 43
RECIST	Response Evaluation Criteria in Solid Tumors
PP	Per Protocol
PT	Preferred Term
RBC	Red Blood Cell
RT	Radiation Therapy
SAE	Serious Adverse Event
SAP	Statistical Analysis Plan
SI	Systeme Internationale
SOC	System Organ Class
SOM	Severe Oral Mucositis
TEAE	Treatment-Emergent Adverse Event
UOM	Ulcerative Oral Mucositis
WBC	White Blood Cell
WHO	World Health Organization
WHO Drug	World Health Organization Drug Dictionary

## INTRODUCTION

This statistical analysis plan (SAP) provides a more technical and detailed elaboration of the statistical analyses of efficacy and safety as outlined and/or specified in the study protocol. Specifications of tables, figures, and data listings are contained in a separate document (table shells).

## 1 STUDY OBJECTIVES

#### 1.1 PRIMARY OBJECTIVE

• To assess the efficacy of SGX942 (dusquetide) compared to placebo in decreasing the duration of severe oral mucositis (SOM; defined as World Health Organization [WHO] Grade lesion ≥3) through 6-week post-RT in patients receiving fractionated radiation treatments and concomitant cisplatin chemotherapy, given as 80-100 mg/m² every third week, for the treatment of squamous cell carcinoma of the oral cavity or oropharynx.

#### 1.2 SECONDARY OBJECTIVES

## 1.2.1 Clinically Important Secondary Objectives

- 1. To assess the impact that SGX942 has on the Area-Under-the-Curve (AUC) for SOM (WHO Grade ≥3) by time plot (severity-weighted duration)
- 2. To assess the impact that SGX942 has on the Area-Under-the-Curve (AUC) for ulcerative oral mucositis (UOM; defined as WHO Grade ≥2) by time plot (severity-weighted duration)
- 3. To assess the impact that SGX942 has on the incidence of SOM
- 4. To assess the impact that SGX942 has on the quality of life assessment using the European Organization for Research and Treatment of Cancer (EORTC) QLQ-C30 (version 3) and QLQ-H&N43 instrument
- 5. To assess the impact that SGX942 has on the amount of opioids used

## 1.2.2 Additional Secondary Objectives

- To assess the impact that SGX942 has on the cumulative number of days of RT breaks
- To assess the impact that SGX942 has on the duration of SOM; in all randomized patients receiving fractionated RT and concomitant cisplatin chemotherapy, given as 80-100 mg/m^2
- To assess the impact that SGX942 has on the duration of UOM
- To assess the impact that SGX942 has on the cumulative amount of pain reported by patients

## 1.3 SAFETY OBJECTIVES

- To assess the impact that SGX942 has on the Adverse Events (AE) and Serious Adverse Events (SAE)
- To assess the impact that SGX942 has on changes in safety laboratory values
- To assess the impact that SGX942 has on the Response Evaluation Criteria in Solid Tumors (RECIST) categorization of the primary tumor at 12 weeks and 12 months post chemoradiation therapy (CRT)
- To assess the impact of SGX942 on the incidence of reported presumed bacterial infections between Baseline and 6 weeks after completion of radiation therapy (RT) by total number and by severity of infection, graded using the National Cancer Institute's (NCI's) Common Terminology Criteria for Adverse Events (CTCAE)

- To assess the impact of SGX942 on 12 month all-cause mortality
- To assess the impact of SGX942 on progression free survival through 12 months

#### 2 STUDY DESIGN

Approximately 260 patients will be enrolled into this Phase 3, placebo-controlled, double-blind, multinational study to evaluate the efficacy of SGX942 compared to placebo in treating the duration of SOM in patients receiving chemoradiation therapy (CRT) for the treatment of head and neck cancer (HNC). The study sample size takes into account the recommendation of the study Data Monitoring Committee (DMC) to increase the study sample size to 260 subjects. Up to an additional 10% may be enrolled to offset the impact of study dropouts (i.e., those subjects that do not receive 55 Gy radiation) and missing data which are each expected to potentially increase during the COVID-19 pandemic.

Patients will be randomized into one of two groups (1.5 mg/kg SGX942:Placebo) at a 1:1 ratio. They will be stratified by site, presence of gastrostomy tube, and human papilloma virus (HPV) status. Patients will receive their initial blinded intravenous (IV) study drug (1.5 mg/kg SGX942 or placebo) within 3 days following the initiation of RT.

The primary efficacy outcome for this study is the duration of SOM, defined as the number of days from the first oral examination with a WHO Grade assessment of 3 or 4 through the first day that a WHO Grade of <3 is recorded with no subsequent assessments ≥3 through the 6-week post-RT visit. Oral mucositis (OM) will be evaluated using the WHO score for OM.

[figure not shown]
Patients will be screened to assess their eligibility prior to randomization. After randomization, subjects will begin treatment with study drug within 3 days following the initiation of RT.

Patients will receive study drug while undergoing CRT and continue to receive study drug for 2 weeks after the completion of their RT. Dosing will be twice weekly. Study visit days will be every third day (+/-1 day). On study visit days, patients will receive the 4-minute infusion of study drug. Study drug will not be given on the same day as chemotherapy. Study drug can be given at any time during the visit day, but must occur on the same calendar day that is the study visit day. The twice weekly study drug treatment visit calendar extends to 2 weeks post-completion of RT.

Efficacy will be further assessed at the 3 through 6 weeks post-RT completion visits. Follow-up visits will be conducted at 6 and 12 months after the last radiation dose to continue to evaluate safety and secondary endpoints.

Figure 1 summarizes the overall study design and Table 1 outlines the study schedule of procedures and assessments. The study week designations assume a 7-week CRT schedule. These times may require adjustment (as described below) if the treatment course is shorter or if treatment breaks prolong the CRT for more than 7 weeks.

Figure 1: Study Schema

**Table 1: Schedule of Events by Week** 

Study week	Screen	Base 	1w 	2w	3w	4w	5w	6w	7 w	8w	9w	10w	11w	12w	13w	15- 55 w	19w	59w
Post-RT 										1w	2w	3w	4w	5w 	6w	2m-11 m 	12w	12m
Medical History	X	X	2X	2X	2X	2X	2X	2X	2X	2X	2X	X	X	X	X	X	X	X
Informed Consent	X																	
Randomization		X																
History of Pain and Opioid Use		X	2X	2X	2X	2X	2X	2X	2X	2X	2X	X	X	X	X		X	X
Assessment of Infections		X	2X	2X	2X	2X	2X	2X	2X	2X	2X	X	X	X	X			
Radiation 			5X	5X	5X	5X	5X	5X	5X									
Cisplatin 			X			X			X									
Administer Drug			2X	2X	2X	2X	2X	2X	2X	2X	2X							
WHO OM 		X	2X	2X	2X	2X	2X	2X	2X	2X	2X	X	X	X	X			
PEG Tube Use		X	2X	2X	2X	2X	2X	2X	2X	2X	2X	X	X	X	X			
VS 	X	X	2X	2X	2X	2X	2X	2X	2X	2X	2X	X	X	X	X			
Physical Exam	X	X									X 				X			
Safety Labs 	X	X 			X			X			X 		X		X			
AEs		X	2X	2X	2X	2X	2X	2X	2X	2X	2X	X	X	X	X			
Tumor Scan 	X 																X	X
Serum Pregnancy	X	X 													X			
HPV Status	X 																	
Quality of Life		X				X					X 							

<sup>1 Post-RT = time from the last radiation therapy treatment

<sup>2 Baseline information needs to be obtained prior to (0 to 96 hours before) the first dose of study drug

 $^{3}$  w = weeks

<sup>4Only to be done if WHO score is ≥2 at Week 4 Post-RT visit

<sup>5 m = months; patient contact (clinic visit, telephone, or email) required monthly through the 12-month clinic visit

<sup>6 Timing of radiation and chemotherapy at discretion of primary care physicians

<sup>7 WHO OM = oral mucositis grading with WHO Oral Mucositis Grading system

<sup>8 Vital signs to include temperature, weight, pulse, respirations, and seated blood pressure; Height will be obtained at Baseline only

<sup>9 Safety labs = hematology and clinical chemistry panels

Scan = obtain initial staging CT/PET/MRI scans (screening scan must be within 6 weeks prior to Baseline)
 Need to confirm that the initial diagnostic scans were CT, PET, or MRI and the tumor was tested for HPV status

 Repeat test required if Baseline sample >7 days from Screening 13 To be done only on the second visit in week 2 post-RT

#### 2.1 PRIMARY EFFICACY ENDPOINT

The primary efficacy outcome for this study is the duration of SOM through the 6-week post-RT visit, defined as the number of days from the first oral examination with a WHO Grade assessment of  $\geq 3$  until the first time the patient has a WHO Grade of  $\leq 3$  is recorded with no subsequent readings  $\geq 3$ . (mITT population).

#### 2.2 SECONDARY EFFICACY ENDPOINTS

## 2.2.1 Hierarchical Sequential Secondary Endpoints

Multiple endpoints in this trial are expected to be clinically important. To maintain the nominal p-value, the following five secondary endpoints will be tested in a fixed sequence, hierarchical test procedure. In this procedure, a sequential comparison of the groups for each endpoint will be calculated with unadjusted p-values. If the test is statistically significant, the null-hypothesis that the groups are the same will be rejected and testing of the next endpoint will be done. Once an analysis has a p-value above the threshold, no further endpoints will be formally tested. All 5 analyses will be conducted in the mITT population.

- 1. Comparison of the AUC for SOM (WHO Grade ≥3) by time plot (severity-weighted duration)
- 2. Comparison of the AUC for UOM (defined as WHO Grade ≥2) by time plot (severity-weighted duration)
- 3. Comparison of the incidence of SOM
- 4. Comparison of the quality of life assessment using the EORTC QLQ-C30 and QLQ-H&N43 instrument
- 5. Comparison of the total amount of opioids used

### 2.2.2 Other Secondary Endpoints

- Comparison of the cumulative number of days of RT breaks (mITT population)
- Comparison of the duration of SOM; in all randomized patients receiving fractionated RT and concomitant cisplatin chemotherapy, given as 80-100 mg/m² (ITT population)
- Comparison of the duration of UOM (mITT population)
- Comparison of the cumulative amount of pain reported by patients (mITT population)

### 2.3 SAFETY ENDPOINTS

- Comparison of the incidence, type, and body system categorization of AEs
- Comparison of the incidence, type, and body system categorization of SAEs
- Comparison of the changes from Baseline for hematology parameters, clinical chemistry parameters, and vital signs
- Comparison of tumor status at 12 weeks and 12 months following completion of RT categorized using the RECIST [1.1] criteria
- Comparison of the incidence and severity of reported infections assessed by CTCAE grading
- Comparison of all-cause mortality through 12 months follow-up
- Comparison of progression-free survival through 12 months follow-up

## 2.4 STUDY ENDPOINT DEFINITION

## 2.4.1 Oral Mucositis (OM) Grading

OM will be evaluated by personnel trained in the use of the WHO Oral Mucositis Grading system which includes both physical and functional information. This grading system is widely utilized in OM clinical research trials including the SGX942 Phase 2 trial and is shown in Table 2.

**Table 2: WHO Oral Mucositis Grading System** 

Score	Findings
0	No findings OR Pain or erythema (not both)
1	Pain and erythema AND No ulcer
2	Ulcer and/or pseudomembrane, AND Able to eat solid food AND Able to drink
3	Ulcer and/or pseudomembrane, AND Not able to eat solid food AND Able to drink
4	Ulcer and/or pseudomembrane, AND Not able to eat solid food AND Not able to drink

Only medical personnel at the site who have undergone training and certification in using the WHO Grading system will perform the OM assessments.

#### 2.4.2 Tumor Status

The tumor response to treatment will be used as a safety endpoint. Results at 12 weeks and 12 months post-RT will be compared to the Screening results using the RECIST 1.1 system. The evaluation criteria for the target lesion (the primary head and neck carcinoma) are shown in Table 3; the criteria for non-target lesions are shown in Table 4; and the criteria for overall categorization of the tumor status are shown in Table 5. In addition, details pertaining to recurrence of disease, additional therapy, or surgery required after the active treatment phase of the trial is completed will be collected and recorded in the electronic case report form (eCRF) throughout all follow up visits until 12 months (±28 days) following the last RT treatment.

**Table 3: RECIST Evaluation of the Target Lesion** 

Target Lesion Response	Measurement
Complete Response (CR)	All target lesions gone
Partial Response (PR)	>30% decrease from baseline
Progressive Disease	>20% increase from smallest sum of longest diameter recorded since treatment started (best response)
Stable Disease (SD)	Neither Progressive Disease nor Partial Response

**Table 4: RECIST Evaluation of the Non-target Lesion** 

Target Lesion Response	Measurement	
Complete Response (CR)	All non-target lesions gone Tumor markers gone	
Stable Disease (SD)	Persistence of ≥1 non-target lesion Tumor marker level elevated	
Progressive Disease	Enlargement of non-target lesions	

**Table 5: Overall RECIST Response** 

Target Lesions	Non-target Lesions	New Lesions	Overall Response
CR	CR	No	Complete Response
CR	SD	No	Partial Response
PR	Non-Progressive Disease	No	Partial Response
SD	Non-Progressive Disease	No	Stable Disease
Progressive Disease	Any	Yes or No	Progressive Disease
Any	Progressive Disease	Yes or No	Progressive Disease
Any	Any	Yes	Progressive Disease

## 3 STATISTICAL CONSIDERATIONS

#### 3.1 SAMPLE SIZE CALCULATION

Sample size assessments are based on testing the hypothesis of superiority with a two-sample log rank test using the median duration of SOM, an equal allocation ratio, a 90% power (1- $\beta$ ), and an  $\alpha$  level of 0.05. In the Phase 2 clinical trial, the median duration of SOM was 30 days in the placebo group and 10 days in the 1.5 mg/kg SGX942 treatment group. Because of the variability of reported results for SOM in the patient population, a conservative assumption was made that the median duration of SOM among patients receiving a minimum of 55 Gy of cumulative radiation will be 13 days in the placebo group and 8

days in the SGX942 group. Using this assumption, approximately 95 evaluable patients per arm (190 patients total) were to be randomized.

#### 3.2 ANALYSIS POPULATIONS

## 3.2.1 Safety Population

The safety population is defined as all subjects who received at least one dose of study drug. Subjects will be analyzed based on the treatment received.

## 3.2.2 Intent-to-treat (ITT) Population

The ITT population is defined as all subjects who were randomized to study drug and received at least one dose of study drug. Subjects will be analyzed based on the treatment assigned.

## 3.2.3 Modified Intent-to-treat (mITT) Population

The mITT population is defined as all randomized subjects who received at least one dose of study drug and at least 55 Gy of cumulative radiation therapy. Subjects will be analyzed based on the treatment assigned.

## 3.2.4 Per Protocol (PP) Population

The PP population is defined as all randomized patients who received at least a 55 Gy cumulative dose of radiation and at least 10 doses of study drug without major or important protocol deviations. Subjects will be analyzed based on the treatment received.

Major or important protocol deviations are defined as follows:

- Received any of the following prohibited concomitant medications during the active-treatment portion of the trial (baseline through 6 weeks post-radiation treatment):
  - o GM-CSF (e.g., Leukine®)
  - o IL-11 (e.g., Neumega®)
  - Low level laser therapy
  - Other investigational agents for mucositis
- Had breaks in study drug administration of more than 8 days between successive doses, including any final missed doses
- · Received any incorrect study drug vial treatments

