- To assess the impact that SGX942 has on the cumulative amount of pain reported by patients
- The duration of SOM using an alternative definition calculated as the number of days from the first oral examination with WHO grade ≥3 through the last assessment with a WHO score ≥3 (and not to the first assessment with a WHO grade <3) with no further reports of a WHO grade >3.
- The duration of SOM in the Per-Protocol Population defined as patients receiving a cumulative radiation dose of at least 55 Gy and having received all study drug scheduled.

Safety Objective:

Safety objectives will include the following:

- To assess the impact that SGX942 has on the Adverse Events (AE) and serious Adverse Events (SAE)
- To assess the impact that SGX942 has on changes in safety laboratory values
- To assess the impact that SGX942 has on the Response Evaluation Criteria in Solid Tumors (RECIST) categorization of the primary tumor at 12 weeks and 12 months post-CRT
- To assess the impact of SGX942 on the incidence of reported presumed bacterial infections between Baseline and 6 weeks after completion of radiation therapy (RT) by total number and by severity of infection, graded using the National Cancer Institute's (NCI's) Common Terminology Criteria for Adverse Events (CTCAE)
- To assess the impact of SGX942 on 12 month all-cause mortality
- To assess the impact of SGX942 on progression free survival through 12 months

Methodology:

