Original: 11 January 2017 Confidential Page 6 of 67

Criteria for Evaluation:

Efficacy:

Efficacy will be determined in patients who have received enough radiation exposure to put them at significant risk of developing SOM (defined as a cumulative radiation dose of at least 55 Gy).

Primary Endpoint:

The primary efficacy outcome for this study is the duration of SOM, defined as the number of days from the first oral examination with a WHO Grade assessment of ≥ 3 until the first time the patient has a WHO Grade of ≤ 3 with no subsequent readings ≥ 3 .

Secondary endpoints will be analyzed in hierarchical order:

- The Area-Under-the-Curve (AUC) for SOM (WHO Grade ≥3) by time plot (severity-weighted duration)
- The Area-Under-the-Curve (AUC) for ulcerative oral mucositis (UOM; defined as WHO Grade ≥2) by time plot (severity-weighted duration)
- The incidence of SOM
- 4. The quality of life assessment using the European Organization for Research and Treatment of Cancer (EORTC) Quality of Life Questionnaire 30 question module (EORTC QLQ-C30 (version 3)) and the EORTC Head and Neck Cancer latest 43 question module (QLQ-H&N43) instrument
- 5. The amount of opioids used

The following secondary endpoints will also be examined:

- The cumulative number of days of radiation treatment breaks
- The duration of SOM in all randomized patients receiving fractionated RT and concomitant cisplatin chemotherapy, given as 80-100 mg/m² every third week (ITT population)
- The duration of UOM
- The cumulative amount of pain reported by patients
- The duration of SOM using an alternative definition calculated as the number of days from the first oral examination with WHO grade ≥3 through the last assessment with a WHO score ≥3 (and not to the first assessment with a WHO grade <3) with no further reports of a WHO grade >3.
- The duration of SOM in the Per-Protocol Population defined as patients receiving a cumulative radiation dose of at least 55 Gy and all scheduled study drug.

Safety:

- The incidence, type, and body system categorization of AEs
- The incidence, type, and body system categorization of SAEs
- The changes from Baseline for hematology parameters, clinical chemistry parameters, and vital signs
- Tumor status at 12 weeks and 12 months following completion of RT categorized using the RECIST criteria

Confidential

- The incidence and severity of reported infections assessed by CTCAE grading
- The 12 month post-RT survival

Statistical Methods:

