5.2. Secondary Objectives

To assess the impact of SGX942 compared to placebo on the following clinically important secondary objectives:

- To assess the impact that SGX942 has on the Area-Under-the-Curve (AUC) for SOM (WHO Grade ≥3) by time plot (severity-weighted duration)
- 2. To assess the impact that SGX942 has on the Area-Under-the-Curve (AUC) for ulcerative oral mucositis (UOM; defined as WHO Grade ≥2) by time plot (severity-weighted duration)
- 3. To assess the impact that SGX942 has on the incidence of SOM
- 4. To assess the impact that SGX942 has on the quality of life assessment using the EORTC QLQ-C30 (version 3) and QLQ-H&N43 instrument
- 5. To assess the impact that SGX942 has on the amount of opioids used

To assess the impact of SGX942 compared to placebo on the following additional secondary objectives:

- To assess the impact that SGX942 has on the cumulative number of days of RT breaks
- To assess the impact that SGX942 has on the duration of SOM; in all randomized patients receiving fractionated RT and concomitant cisplatin chemotherapy, given as 80-100 mg/m² (ITT population)
- To assess the impact that SGX942 has on the duration of UOM
- To assess the impact that SGX942 has on the cumulative amount of pain reported by patients
- The duration of SOM using an alternative definition calculated as the number of days from the first oral examination with WHO grade ≥3 through the last assessment with a WHO score ≥3 (and not to the first assessment with a WHO grade <3) with no further reports of a WHO grade ≥3
- The duration of SOM in the Per-Protocol Population defined as patients receiving a cumulative radiation dose of at least 55 Gy and study drug twice per week during and for 2 weeks after radiation therapy

Original: 11 January 2017 Confidential Page 28 of 67

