8.2. Concomitant Medications

Subjects will be treated on an outpatient basis. If patients require hospitalization for non-study related complications of therapy, all possible study procedures will be performed. RT and assessment of tumor burden in all subjects will be conducted as clinically appropriate, following study-specified protocols. All subjects will receive concomitant cisplatin chemotherapy (80-100 mg/m²) for treatment of cancer of the oral cavity and oropharynx.

Concomitant drugs taken by the patient during the treatment phase and through the 6-week post-RT visit should be recorded in the eCRF. In general, the generic name of the drug should be used. Drug names, especially combination preparations, should not include the dose of each component drug in the name but should be noted in the dose-Name: "Docusate/Senna" Dose "50/8.6" rather than Name: "Docusate 50 mg - Senna 8.6 mg". Components of any mouthwash prescribed should be listed- instead of "Magic Mouthwash" recorded "Mouthwash-Maalox/Lidocaine".

The following medications/therapies should *NOT* be used in enrolled patients (from baseline through 6 weeks post-RT):

- Amifostine (Ethyol®)
- Benzydamine hydrochloride
- Cetuximab (Erbitux®)
- Cevimeline hydrochloride (Evoxac[®])
- Glutamine as a prophylactic agent for mucositis
- · Devices for mucositis including GelClair, MuGard, Episil and Caphosol
- GM-CSF (e.g., Leukine[®])
- IL-11 (Neumega[®])
- 'Magic mouthwash', 'Miracle mouthwash' or other mouthwash solutions containing any of the following:

Confidential

- Chlorhexidine
- Hydrogen peroxide
- Diphenhydramine

- Tetracycline
- Palifermin (Kepivance[®]) or other keratinocyte or fibroblast growth factor
- Pilocarpine hydrochloride (Salagen[®])
- Povidone-iodine rinses
- Steroid rinses
- Sucralfate in suspension form (use of sucralfate tablets is not proscribed)
- Other biologic response modifiers except hematopoietic growth factors for the management of anemia or myelosuppression
- Low level laser therapy
- Other investigational agents for mucositis

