10.2.2.6. Duration of SOM in the Per-Protocol Population

The duration of SOM in the Per-Protocol Population defined as patients receiving a cumulative radiation dose of at least 55 Gy and having received all scheduled study drug doses.

Confidential

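### The protocol and the SAP define the per-protocol set by two different rules, and the SAP rule does not exclude for most of the therapies the protocol prohibits

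*SAP*

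**What the plan says.** **Protocol.** Duration of SOM in the PP set is one of the additional secondary endpoints. Section 10.2.2.6 defines the set as "patients receiving a cumulative radiation dose of at least 55 Gy and having received all scheduled study drug doses". The synopsis says the same under objectives ("having received all study drug scheduled") and under endpoints ("cumulative radiation dose of at least 55 Gy and all scheduled study drug"). Section 5.2 words the dosing condition as "study drug twice per week during and for 2 weeks after radiation therapy". None of these places excludes a patient for prohibited treatment. Section 8.2 separately lists therapies that enrolled patients should not receive from baseline to 6 weeks after radiotherapy (RT), for example "Devices for mucositis including GelClair, MuGard, Episil and Caphosol".

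**SAP.** Section 3.2.4 requires at least 55 Gy and "at least 10 doses of study drug without major or important protocol deviations". It then defines those deviations by a closed list:
- receipt of GM-CSF, IL-11, low level laser therapy or another investigational mucositis agent;
- a dosing-gap rule ("Had breaks in study drug administration of more than 8 days between successive doses, including any final missed doses");
- any incorrect vial.

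SAP 5 gives a second, open-ended list of major deviations, which includes eligibility failures. SAP 9 uses the PP set for sensitivity analyses. The secondary lists in SAP 2.2.2 and 9.3.2 do not contain a PP endpoint.

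**The concern.** One label stands for two populations. A programmer who follows the SAP exactly will not produce the endpoint that the protocol lists.

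A per-protocol analysis is meant to show the effect in patients treated as planned, without other treatment that could alter the outcome. The SAP set can hold patients who missed a substantial share of their doses. It can also hold patients given palifermin, amifostine, benzydamine, a mucositis device or steroid rinses, all of which the protocol bars.

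Two features of the documents give this some weight. Protocol 4.5 cites agreement between the PP, mITT and ITT results as a reason for confidence in the Phase 2 trial, so agreement with the PP set is evidence the sponsor relies on. SAP Appendix 1, item 5, says that the pandemic affected the number and degree of protocol deviations, so the rule chosen may move real patients in or out.

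**Working it through.** **1. The definitions side by side.**

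| Condition | Protocol (synopsis, 5.2, 10.2.2.6) | SAP 3.2.4 |
|---|---|---|
| Radiation | at least 55 Gy | at least 55 Gy |
| Doses | all scheduled | at least 10 |
| Dosing gap | not stated | over 8 days excludes, final missed doses counted |
| Prohibited therapy | not stated | four items exclude |
| Wrong vial | not stated | excludes |

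The protocol has two wordings but one rule. Its dosing calendar is itself twice weekly to 2 weeks after RT (Protocol 6.1 and 8.1), so full twice-weekly dosing and all scheduled doses mean the same thing.

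**2. Share of planned doses.** Planned doses = 2 × (RT weeks + 2). The synopsis gives 5 to 7 weeks as the typical RT course. This fits 55/2.2 = 25 to 72/2.0 = 36 fractions at five per week.
- 5 weeks: 2 × 7 = 14; 10/14 = 71%
- 6 weeks: 2 × 8 = 16; 10/16 = 63%
- 7 weeks: 2 × 9 = 18, matching the schedule table; 10/18 = 56%

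The synopsis also expects 6 to 11 weeks of study drug. At 11 weeks with RT breaks, 10/22 = 45%. At 6 weeks, 10/12 = 83%, but that implies 4 weeks of RT, at most 4 × 5 × 2.2 = 44 Gy, which is below the 55 Gy that both rules require.

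**3. What the gap rule removes.** Assume alternating 3- and 4-day spacing, the first dose given, and the final gap measured to the last scheduled dose.
- One missed dose leaves 3 + 4 = 7 days, which is allowed.
- Two adjacent missed doses leave 10 or 11 days, which excludes.
- Stopping after dose 10 of 18 leaves 59 − 31 = 28 days, which excludes. With 16 or 14 planned doses the final gap is 21 or 14 days, which also excludes.
- Enumeration of the 18-dose calendar finds 129 patterns of exactly 10 doses that qualify. So 10 of 18 can be reached, mainly through scattered single misses. The count shows that it is possible, not how often it would happen.

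**4. Prohibited therapies.** Protocol 8.2 has 17 top-level items and SAP 3.2.4 names 4 of them, so 17 − 4 = 13 (13/17 = 76%) do not exclude. The 13 are amifostine, benzydamine, cetuximab, cevimeline, prophylactic glutamine, mucositis devices, the listed mouthwashes, palifermin and similar growth factors, pilocarpine, povidone-iodine rinses, steroid rinses, sucralfate suspension and other biologic response modifiers. If cetuximab, cevimeline and pilocarpine are set aside as arguably not mucositis therapies (an assumption), 10 of 14 (71%) do not exclude.

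**5. Neither set contains the other.** A patient with 17 of 18 doses and no listed deviation is in the SAP set and outside the protocol set. A patient with all 18 doses who also had low level laser therapy is in the protocol set and outside the SAP set.

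**The case against.** The best defence is that little depends on this. The primary endpoint and all five hierarchical secondary endpoints are tested in the mITT set. PP duration of SOM is an unranked secondary endpoint in the protocol and a sensitivity analysis in the SAP, and no alpha is attached to it. That stands, and it limits the point to a supportive analysis.

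The SAP is also not simply the looser document. It is looser on doses but stricter on therapies and vials, because the protocol's PP wording excludes nobody for either. Requiring every dose would drop a patient for one missed visit, so a lower floor is defensible. The Phase 2 mITT definition in Protocol 4.5 also used 10 doses, although the documents do not say that the figure was carried over.

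Three stronger readings are tempting, and the documents do not support them:
- **Three conflicting definitions.** There are three wordings across the two documents but only two rules, as step 1 shows.
- **Weekly dosing qualifies.** It meets the 8-day limit, but over 7, 8 or 9 treatment weeks it gives about 7, 8 or 9 doses and fails the floor of 10. It passes only if breaks stretch treatment to about 10 or 11 weeks.
- **The definition can be picked after the results are seen.** Protocol 12.1 defers the details of analysis to the SAP, and SAP 3.2.4 is explicit. What remains is that the protocol's definition was never withdrawn, and that SAP 5 uses the word major in a different sense.

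**Conclusion.** The contradiction holds. The protocol's listed PP endpoint rests on full dosing. The SAP's PP set rests on a 10-dose floor, which is 71%, 63% or 56% of planned doses for 5, 6 or 7 weeks of RT, tempered by a gap rule that removes most early stoppers and most block misses. Under the SAP, 13 of the 17 prohibited items (or 10 of 14 on the narrower count) do not exclude, and no reason is given for choosing the other four.

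A reader might infer that the PP result is therefore biased, or would change materially with the rule. The documents do not support that. They give no rates of missed doses or of prohibited-therapy use, so neither the size nor the direction of any change can be calculated. The primary and hierarchical analyses are unaffected.

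The dose shares assume twice-weekly dosing without RT breaks. The gap findings assume regular 3- and 4-day spacing; with the permitted 2 to 4 days between doses, some short block misses could also pass.

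**What to change.** Before unblinding:
1. Reconcile Protocol 5.2 and 10.2.2.6, and the synopsis, with SAP 3.2.4 so that one rule carries the PP label for the listed endpoint. Report the other dose rule as a separately named sensitivity set. Which threshold takes the label is a matter of judgement for the sponsor to state and justify.
2. Make the concomitant-therapy exclusion in SAP 3.2.4 refer to the prohibited list in Protocol 8.2, or name the items left out and say why.
3. Align the major-deviation lists in SAP 3.2.4 and SAP 5, so that it is clear whether, for example, an eligibility failure removes a patient from the PP set.

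The cost is SAP wording (with a matching protocol correction if the SAP's rule takes the label), one extra analysis run and a smaller PP set. How much smaller cannot be estimated from the documents.
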